Title: Digital Escape Room Game for Hypovolemic Shock Management: A Mixed-Methods Study in Nursing Education

NCT number: NCT07204899

Date of the document (reviewed by a human subjects protection review board): 6.05.2025

Study Protocol:

Methods

Study design

This study employed an explanatory sequential mixed-methods design. A randomized controlled trial design was used in the quantitative phase. The experimental group participated in an online escape room intervention, while the control group received traditional lecture-based instruction. Quantitative data were collected to evaluate the effect of the intervention on students' knowledge level and satisfaction.

Following the quantitative phase, a purposive sample of students from the experimental group was invited to participate in focus group interviews. The qualitative phase was conducted to explore students' perceptions and experiences in greater depth, providing contextual insights into the mechanisms underlying the quantitative results. Integrating the two phases allowed for a more comprehensive understanding of the educational impact of the online escape room intervention, combining measurable outcomes with rich narrative accounts.

Setting and participants

The study was conducted between June and July 2025 with third-year nursing students enrolled at a foundation university in Ankara, Türkiye. Students were invited to participate through an in-class announcement, and the inclusion criterion was being a third-year nursing student who provided informed consent.

Power analysis was performed using G*Power 3.1 (F tests, repeated measures ANOVA—between-group effect). Based on two groups and three measurement points, a

repeated measures correlation of 0.50, an effect size of $f=0.35$, a two-way $\alpha=0.05$, and a power of $1-\beta=0.80$, the required total sample size was calculated as $N=46$ (23 participants in each group). Considering possible attrition, a total sample size of 30 participants was planned for each group. Accordingly, 58 volunteer students were recruited for the quantitative phase and randomly assigned to either the intervention or control groups. For the qualitative phase, 12 students were purposively selected from among those who had participated in the quantitative phase. In addition, nurse educators with at least five years of experience in teaching and mentoring students were included as participants. Data collection for the qualitative phase was carried out through focus group interviews and continued until no new themes emerged, indicating thematic saturation.

Randomisation and Blinding

Eligible participants were randomly assigned to either the experimental group, which received the digital escape room game intervention, or the control group, which received traditional classroom-based education, in a 1:1 allocation ratio. Randomisation was performed using an online random sequence generator (Research Randomizer, <https://www.randomizer.org/>) by an independent statistician who was not involved in participant recruitment, intervention delivery, or outcome assessment.

Given the nature of the interventions, blinding of participants and facilitators was not feasible. However, to minimise performance and detection bias, outcome assessors and data analysts remained blinded to group allocation throughout the study. All data were coded anonymously, and statistical analyses were conducted using coded identifiers (Group A/Group B) until the final interpretation phase.

Pre-application of the study

A preliminary application was undertaken to assess the clarity, feasibility, and functionality of both the data collection instruments and the digital escape room game. This

stage was conducted with 10 fourth-year nursing students enrolled in the 2024–2025 academic year. Participants were asked to complete the data collection forms, engage with the escape room game, and provide structured feedback regarding the comprehensibility of the forms, the usability of the game design, and the alignment of tasks with the intended learning outcomes.

Based on the feedback obtained, minor revisions were made to enhance the precision of the data collection tools and to optimize the flow and instructional components of the game. Following these adjustments, both the instruments and the game were finalized for the main study. To maintain methodological rigor and avoid potential bias, students who participated in the pre-application were excluded from the final sample.

Implementation phase of the study

All students who agreed to participate first completed the Sociodemographic Information Form, followed by the Hypovolemic Shock Information Form as a pretest. After the pretest, all participants received a two-hour traditional lecture on hypovolemic shock and nursing management. The lecture covered the following topics: definition, etiology and risk factors, pathophysiology, clinical findings and diagnosis, medical treatment approaches, nursing care and processes, nursing diagnoses and interventions, patient education, and psychosocial support. Students were then randomly assigned to either the intervention or control group, ensuring comparable mean pretest knowledge scores.

Control Group (n = 28): In addition to the two-hour theoretical training, no further intervention was provided. Immediately after the lecture and again one month later, students completed the Hypovolemic Shock Information Form as a posttest. After completion of the study, control group participants were also given the opportunity to experience the digital escape room game.

Intervention Group (n = 27): Following the pretest and theoretical training, students played a digital escape room game on hypovolemic shock and nursing management developed

by the researchers using the *Genially* platform. The design and procedures of the game are detailed in the “Experimental procedure” section. Immediately after the intervention and again one month later, students completed the Hypovolemic Shock Information Form as a posttest. In addition, the GAMEX (Game Experience) Scale was administered, and a subset of students participated in a focus group interview.

Experimental procedure

This study was conducted with third-year undergraduate nursing students to evaluate knowledge and management of hypovolemic shock. It comprised two stages: (1) development and implementation of the HYPSEM ERG, and (2) testing the game and assessing outcomes.

Stage 1: The HYPSEM (HYPovolemic Shock EMergencies) ERG was developed, introduced to students, and made available for one week.

Stage 2: Upon completion, students’ knowledge and satisfaction were evaluated.

HYPSEM game procedure

HYPSEM is a web-based digital escape room addressing hypovolemic shock (HVS). It was designed to examine whether escape rooms enhance motivation to learn about HVS. Development on the *Genially* platform enabled the creation of interactive click-and-point rooms, fostering engagement. Hosting the game online ensured universal access without spatial or temporal constraints.

Implementation proceeded as follows:

- Students first received a face-to-face briefing in which the designer introduced escape rooms, explained the *Genially* platform, and outlined the collaborative structure of the game.
- They were then given one week to play individually at their convenience.

- The designer shared contact information to provide technical support. Students could request unlimited hints and were reassured that feedback would be available even without prior experience.
- After successfully completing the final test and exiting the escape room, students filled out a post-test questionnaire.

Escape room design

HYPSEM simulates a hospital room scenario involving a patient with hypovolemic shock, requiring students to access essential information from the patient's file to prevent adverse outcomes. The game can be accessed via *Genially* (<https://view.genially.com/685bc3f26dbc4e0ec352beb0/interactive-content-hastaneden-kacis-oyunu>).

Students had 15-20 minutes to solve six puzzles. Content aligned with prior lectures, practice sessions, and case studies; no new information was introduced during gameplay to facilitate smooth progression. Access was provided via QR code. The game opened with a clinical narrative, followed by rules, instructions, and symbol explanations.

The puzzles included multiple-choice, true/false, sequencing, and clinical reasoning tasks related to shock type, stage, management, and nursing interventions. Clues were drawn from patient files, physical examination findings, laboratory results, and vital signs. Incorrect responses triggered warning signals as feedback. A countdown timer imposed time constraints, and hints were embedded in items such as the patient file, behind a door, an electrocardiograph, a medication bag, and above a cupboard. Successful management of the patient and hospital exit designated students as “heroes.” Students could replay the game without restriction during the one-week study period.

Data collection

Data were collected face-to-face and via Google Forms between June 2 and July 20, 2025. In this study, multiple instruments were employed to assess students' knowledge of shock management, their satisfaction with the game, and their perceptions of the digital escape room.

Quantitative data

Sociodemographic Information Form

Sociodemographic data, including participants' age, gender, and prior experiences, were collected using a form developed by the researchers based on the literature (Bonaduce, 2024; Sat et al., 2025).

Hypovolemic Shock Information Form

A 20-item true-false test was administered to measure students' theoretical knowledge of hypovolemic shock. The form was reviewed by seven field experts to establish content validity and was administered both as a pretest and a posttest.

GAMEX (Game Experience) Scale

Students' experiences with the digital escape room were evaluated using the 27-item, 5-point Likert-type GAMEX scale (Eppman et al., 2018). The instrument comprises six subscales: enjoyment, absorption, creative thinking, involvement, absence of negative effects, and dominance. The Turkish adaptation was validated and found reliable by Arıkan Dönmez et al. (2024). Scale scores range from 27 to 135, with higher scores indicating a more positive gaming experience. Cronbach's alpha was 0.93 for the total scale, and subscale alphas ranged from 0.67 to 0.929.

Qualitative data

Focus group discussions with students and facilitators were organized within one week after the completion of the HYPSEM game. The sessions were held via the Zoom video conferencing platform and followed a semi-structured interview form. Three female researchers with expertise in qualitative research served as moderators to ensure both consistency and depth

of the discussions. The interview form consisted of four open-ended questions addressing participants' expectations prior to the game and whether these were fulfilled, the emotions they experienced during the activity, the game's contribution to their learning (e.g., knowledge, practical skills, decision-making), and their opinions on the broader use of digital escape room games in nursing education. The discussions explored not only students' experiences and perceptions of the usefulness of the HYPSEM game, but also their suggestions for areas of improvement. Each focus group included three to five participants and lasted between 45 and 80 minutes. All sessions were audio-recorded and subsequently transcribed verbatim.

Statistical Analysis Plan (SAP):

Quantitative data analyses were conducted using IBM SPSS Statistics version 25. Descriptive statistics (mean, standard deviation, minimum, and maximum) were calculated for all study variables. The internal consistency of the GAMEX scale and its subdimensions was assessed using Cronbach's α coefficients.

To evaluate baseline equivalence between groups, independent samples t -tests were performed. The effectiveness of the intervention over time was examined using a repeated-measures analysis of variance (ANOVA) with one within-subjects factor (time: pre-test, post-test 1, post-test 2) and one between-subjects factor (group: GAMEX vs. control). Mauchly's test of sphericity was applied to verify the assumption of sphericity, and where violations occurred, the Greenhouse-Geisser correction was used. Effect sizes for ANOVA results were reported as partial η^2 .

In addition, Bonferroni-adjusted pairwise comparisons were conducted to explore differences across the three time points within each group. Independent samples t -tests were also carried out at each measurement point to assess between-group differences. For these comparisons, Cohen's d values were calculated to estimate the magnitude of differences (0.2 = small, 0.5 = medium, 0.8 = large). Statistical significance was set at $p < .05$ for all analyses.

Qualitative data were derived from audio-recorded focus group discussions, which were transcribed verbatim and analyzed thematically following Braun and Clarke's (2006) six-phase framework: (1) familiarization with the data, (2) generating initial codes, (3) searching for themes, (4) reviewing themes, (5) defining and naming themes, and (6) producing the report. Coding was independently conducted by two researchers using MAXQDA Analytics Pro 2022 software. Codes were then grouped into subthemes based on similarities, and consensus was reached through regular discussions and deliberations. A third researcher verified themes, and the entire research team engaged in reflective discussions to enhance interpretive rigor. To ensure trustworthiness, Lincoln and Guba's (1985) criteria were applied: credibility through peer debriefing and researcher triangulation; dependability through independent coding; confirmability via detailed documentation and audit trails; and transferability through thick description of the study context and the inclusion of direct participant quotations. Data collection and analysis were concluded once thematic saturation was reached.

Mixed methods analysis/Data triangulation /Data integration

After separately analyzing quantitative and qualitative data, integration was carried out to achieve a comprehensive understanding of the research problem. Mixed methods integration enables the examination of convergence and complementarity between different forms of evidence, thereby increasing the validity and robustness of the study (Creswell & Plano Clark, 2018; Fetters et al., 2013). Data triangulation was employed to mitigate the limitations of relying solely on a single method and to ensure that both measurable outcomes and contextual insights were considered in addressing the research objectives. In this study, integration was pursued not to duplicate findings but to provide methodological rigor, support the credibility of interpretations, and generate a more holistic view of the educational impact of the digital escape room intervention (Guetterman et al., 2015; McCrudden et al., 2021).

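### The 80% power at N=46 belongs to a group main effect that averages in the pretest; f=0.35 then means 1.05 SD at the post-tests, and the effectiveness test should instead adjust for the pretest

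*Combined protocol and SAP*

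**What the plan says.** **Sample size (Methods, Setting and participants).** "Power analysis was performed using G*Power 3.1 (F tests, repeated measures ANOVA—between-group effect". The inputs are two groups, three measurements, a correlation of 0.50 and power 0.80, with "an effect size of $f=0.35$, a two-way $\alpha=0.05". The result: "the required total sample size was calculated as $N=46$ (23 participants in each group". For attrition, "a total sample size of 30 participants was planned for each group"; 58 students were recruited. No score difference or SD is given, and the plan does not say what f=0.35 means at the post-tests.

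**Timing (Implementation phase).** The pretest comes first, then a lecture for everyone, then allocation: "Students were then randomly assigned to either the intervention or control group, ensuring comparable mean pretest knowledge scores". The listed group sizes are 28 (control) and 27 (intervention). Randomisation and Blinding says only: "Randomisation was performed using an online random sequence generator".

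**Analysis (SAP).** Effectiveness over time is examined by a repeated-measures ANOVA with factors group and time (pretest, post-test 1, post-test 2). Independent t-tests between groups are added at each time point. All tests use p < .05. The SAP does not say which ANOVA term decides, and no model has the pretest as a covariate.

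**The concern.** The between-group term compares the two groups on each student's average over all three tests. One of the three was taken before the groups existed, so the game can act on only two thirds of what is tested. The third component adds noise and no signal. An effect size that looks moderate on this average is half as large again at the post-tests, where the effect matters.

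Two things are at stake. A reader who takes 0.70 SD (2 x 0.35) as the assumed effect of the game will misread what the 80% covers. And a pretest already collected from every student is not put to its best use. The ANOVA draws on it only implicitly, through the group x time term, which the SAP does not name as deciding. The t-tests at the post-tests ignore it.

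**Working it through.** **Inputs from the documents:** 2 groups, m=3 tests, rho=0.50, f=0.35, alpha=0.05, N=46; group sizes 28 and 27; pretest before allocation.

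**Assumptions:** equal SDs at all tests; the same correlation between every pair of tests; no expected pretest difference; simple randomisation. For detectable differences, the same difference d (in SDs) at both post-tests.

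**Step 1. The plan's own figure.** For the between-group term, lambda = f² x N x m / (1+(m-1)rho).
- N=46: 0.1225 x 46 x 3/2 = 8.45; power of F(1,44) = 0.811.
- N=44: 0.1225 x 44 x 3/2 = 8.085; power = 0.793.

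So 46 is the smallest balanced total that reaches 80%. The figure reproduces.

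**Step 2. What f=0.35 means at the post-tests.** With two equal groups, f=0.35 is a difference of 2 x 0.35 = 0.70 SD on the three-test average. With zero at the pretest, (0 + D1 + D2)/3 = 0.70, so (D1 + D2)/2 = 0.70 x 3/2 = 1.05 SD. This does not depend on rho. Check: (2 x 1.05/3)² / [(2/3)(1/23+1/23)] = 0.49/0.05797 = 8.45, the same lambda as in Step 1. The SAP's own benchmark calls 0.8 large.

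**Step 3. Difference detectable with 80% power.** Write h = 1/n1 + 1/n2, which is 0.0870 at 23+23 and 0.0728 at 28+27.
- Main effect: lambda = (2d/3)² / [((1+2rho)/3) h], df 1 and N-2.
- Group x time: lambda = (2d²/3) / [(1-rho) h], df 2 and 2(N-2).
- t-test at one post-test: lambda = d²/h, df 1 and N-2.
- Pretest-adjusted (ANCOVA): lambda = d² / [v h (1+F/(N-2))], df 1 and N-3. For the post-test mean, v = (1+rho)/2 - rho² = 0.75 - 0.25 = 0.50. For one post-test, v = 1 - rho² = 0.75. The factor with F, distributed as F(1,N-2), allows for chance pretest imbalance; power is averaged over it.

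| Test | 23+23 | 28+27 |
|---|---|---|
| Group main effect (the one powered) | 1.035 | 0.943 |
| t-test at one post-test | 0.845 | 0.770 |
| Group x time interaction | 0.806 | 0.735 |
| Adjusted, one post-test | 0.741 | 0.673 |
| Adjusted, mean of post-tests | 0.605 | 0.550 |

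**Step 4. Dependence on rho.** At N=46, over rho 0.3 to 0.7, the main effect needs 0.925 to 1.133 SD. The adjusted mean needs 0.632 to 0.507 SD (without the imbalance allowance, which adds about 0.007 at rho=0.50). The ordering holds throughout this range.

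**Step 5. Power at the effect the plan implies.** At 1.05 SD and N=46: main effect 0.811, t-test 0.936, interaction 0.960, adjusted mean 0.998.

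**The case against.** The strongest reply is that nothing here is an error. The power analysis names its test, N=46 is right for it, and at the implied 1.05 SD every planned between-group test at a post-test has at least 0.81 power. The ANOVA also includes the pretest as a level of time, so the group x time term compares change from pretest. A randomised repeated-measures ANOVA with that term named is valid. All of this stands. It limits the point to a diluted target, an untranslated effect size and a less efficient use of the pretest. It does not remove the point, because the powered term is the main effect and the SAP does not name the interaction as deciding.

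Three stronger readings are tempting and not supported.

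- **That the trial is underpowered.** If 0.70 SD at both post-tests had been meant, power at 28+27 would be 0.55 (main effect), 0.72 (t-test) and 0.76 (interaction), against 0.95 for the adjusted mean. The plan nowhere states that effect.
- **That the SAP disregards the pretest.** It does not; only a covariate is missing.
- **That the planned tests miss their 5% level.** If allocation had actually equalised the pretest means, the unadjusted tests would be conservative. But the Implementation phase may only describe loosely what randomisation achieves, and Randomisation and Blinding gives no balancing method. The documents do not settle it.

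A last objection is that moving to a more powerful test after data collection looks like choosing with hindsight. That is fair, and it governs how the change must be made.

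**Conclusion.** The point holds in this form and should be fixed. The sample size is correct for the test named, but that test dilutes the effect of the game by one third. Its f=0.35 corresponds to an unstated average of 1.05 SD at the post-tests. A pretest-adjusted comparison of the same students on the same data detects about 0.60 SD instead of 1.04 SD at 23 per group, and about 0.55 SD instead of 0.94 SD at 28+27.

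The 1.05 SD rests on equal SDs and no expected pretest difference. The detectable differences also rest on the plan's rho=0.50, simple randomisation and an equal effect at both post-tests. None of this shows that more students were needed.

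**What to change.** Make the pretest-adjusted group difference the effectiveness test (ANCOVA, or a mixed model with a common baseline), on the mean of the two post-tests. Give adjusted differences with 95% confidence intervals at each post-test as well. The separate results matter because controls took post-test 1 directly after the lecture, whereas for the game group, "They were then given one week to play individually at their convenience".

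Suggested wording:

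> N=46 was calculated for the between-group main effect; with equal SDs and no expected pretest difference, f=0.35 corresponds to an average of 1.05 SD at the post-tests. The effectiveness test is the pretest-adjusted group difference on the mean of the two post-tests; adjusted differences with 95% confidence intervals are also given at each post-test. With rho=0.50 and allowing for chance pretest imbalance, 80% power is reached at about 0.60 SD (mean) and 0.74 SD (one post-test) with 23 per group, and about 0.55 and 0.67 SD with 28+27.

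If the ANOVA stays the main analysis, name the group x time interaction as the deciding term and state that it has 80% power for about 0.81 SD at N=46 and 0.74 SD at 28+27.

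Reconcile Randomisation and Blinding with the Implementation phase on how comparable pretest means were obtained.

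**Cost.** No students or data are added. The main analysis sentence changes in a study already described in the past tense, so date the change, label it as made after the plan, and report the planned ANOVA beside it. The adjusted mean loses power if the effect fades. With 0.70 SD at post-test 1 and 0.35 SD at post-test 2, its power at 28+27 is 0.76, against 0.62 for the interaction and 0.345 for the main effect. The adjusted test at post-test 1 alone would have 0.83, and at post-test 2 alone 0.31.

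### The protocol says 58 students were randomised but lists arms of 28 and 27, and the SAP defines no analysis set or missing-data rule that would settle who is compared

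*Combined protocol and SAP*

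**What the plan says.** All references are to the combined protocol and SAP.

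- **Setting and participants.** The calculated requirement is 46 students. The plan then allows for losses: "Considering possible attrition, a total sample size of 30 participants was planned for each group". It goes on: "58 volunteer students were recruited for the quantitative phase and randomly assigned to either the intervention or control groups".
- **Randomisation and Blinding.** Assignment was "in a 1:1 allocation ratio".
- **Implementation phase of the study.** The order of events is pretest, lecture, assignment. "All students who agreed to participate first completed the Sociodemographic Information Form, followed by the Hypovolemic Shock Information Form as a pretest". After the lecture, "Students were then randomly assigned to either the intervention or control group, ensuring comparable mean pretest knowledge scores". The next two paragraphs open with "Control Group (n = 28" and "Intervention Group (n = 27". They do not say whether these are numbers allocated, treated or analysed. Both arms take the knowledge form soon after their teaching and again one month later, with no condition attached.
- **HYPSEM game procedure.** The post-test questionnaire is placed after a successful final test and exit from the game. The text does not say whether this is the knowledge form or the GAMEX scale.
- **Statistical Analysis Plan (SAP).** "The effectiveness of the intervention over time was examined using a repeated-measures analysis of variance (ANOVA) with one within-subjects factor", with pretest and two post-tests as the time points and group as the between-subjects factor. Pairwise comparisons within group and t-tests between groups at each time point are added. No analysis population is named, and nothing is said about missing scores.

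**The concern.** The number randomised is a basic fact of a randomised trial, and here it has two values. A reader cannot tell whether the comparison is of the groups as randomised or of the students who returned every form.

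The SAP would normally answer that, and it does not. The plan foresaw attrition, and a one-month follow-up makes missing scores likely, yet no rule covers them. A standard repeated-measures ANOVA drops any student who lacks one of the three scores, while the t-tests at each time point could use everyone present at that time. The two sets of results could then rest on different students.

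If the 3 left after allocation, the protection of randomisation is weakened by an unknown amount in an unknown arm. By the protocol's own sequence everyone took the pretest before assignment, so such students could be described and kept in the analysis.

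**Working it through.** **1. The plan's own sample size.** Inputs from Setting and participants: f = 0.35, m = 3 measurements, correlation 0.50, alpha 0.05, two groups. For the between-group F test, lambda = f² × N × m / (1 + (m − 1) × rho) = 0.1225 × N × 3 / 2 = 0.18375 N, with 1 and N − 2 degrees of freedom.

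| N | lambda | power |
|---|---|---|
| 46 | 8.45 | 0.811 |
| 55 | 10.11 | 0.877 |
| 58 | 10.66 | 0.894 |
| 60 | 11.03 | 0.904 |

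The stated 46 reproduces as the smallest even N with power of at least 0.80. The attrition allowance is 60 − 46 = 14, or 14/60 = 23%.

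**2. The counts.** 28 + 27 = 55; 58 − 55 = 3; 3/58 = 5.2%. The only exclusion in the protocol is of students in the pre-application. They were fourth-years, so they cannot be among third-year volunteers. At 1:1, 58 gives 29/29 and 55 gives 27/28 or 28/27. The listed arms therefore fit 55 allocated with no loss, and also 29/29 with 2 intervention students and 1 control lost.

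**3. Bound on the shift.** Let L_i and L_c be the students lost after allocation from the intervention and control arms. If they depart from their arms' means by 1 SD in opposite directions, the group difference moves by L_i/(27 + L_i) + L_c/(28 + L_c).

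| L_i, L_c | shift (SD) |
|---|---|
| 0, 0 | 0 |
| 1, 0 | 0.036 |
| 1, 1 | 0.070 |
| 0, 3 | 0.097 |
| 3, 0 | 0.100 |
| 1, 2 | 0.102 |
| 2, 1 | 0.103 |

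The planned difference is about 0.70 SD, taking d = 2f.

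**4. What the choice of analysis changes.** This is an illustration, and its inputs are assumptions: 29/29 randomised, no true effect, correlation 0.5 between times, the 2 lowest game performers lost from the intervention arm, 1 control lost at random, lost students having a pretest only. Bias is in SD for the difference at the first post-test. The two figures in each cell are for a correlation of 0.3 and 0.5 between performance and the score named; the third decimal is uncertain by about 2.

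| Loss related to | Single-time t-test | Change from pretest | Mixed model, common pretest mean |
|---|---|---|---|
| post-test 1 | 0.041 / 0.068 | 0.020 / 0.034 | 0.030 / 0.051 |
| all three scores equally | 0.041 / 0.068 | 0.00 / 0.00 | 0.020 / 0.034 |
| pretest only | 0.019 / 0.033 | −0.022 / −0.036 | 0.00 / 0.00 |

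Standard errors are about 0.27 for the t-test and for change (√(1/27 + 1/28) = 0.270; with correlation 0.5 a change score also has SD 1) and about 0.235 for the model. In the first row at 0.5, root mean squared error is √(0.235² + 0.051²) = 0.240 for the model against √(0.27² + 0.034²) = 0.272 for change.

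**The case against.** A harmless reading is open. The pretest and lecture come before assignment, and 28 and 27 are what 1:1 gives for 55, so the 3 may have left before allocation and the sentence with 58 may be a loose summary. This stands as a possibility. The documents do not settle it, and one sentence is still wrong if it is true.

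The SAP nowhere says it will analyse complete cases. That is right: it is an inference from how the standard ANOVA works when no imputation or mixed model is specified.

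Replacing the ANOVA could be called preference, since the mixed model carries more bias than change from pretest in two of the three cases above. The figures stand, so the model should not be presented as a cure. It is still less biased than the single-time t-test throughout and more precise than either alternative. The gain in precision outweighs the small extra bias.

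A reader might infer from the section on the game procedure that intervention students were tested only if they escaped, and that the missing students failed to. The documents do not support this. The questionnaire is not identified, the implementation section sets no such condition, and students had a week with unlimited hints and replays. Nothing shows that anyone failed to exit or went untested for that reason. The two sections need to be reconciled, and no more than that follows.

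**Conclusion.** The point holds in a limited form. The randomised sample size is contradictory as written, the 3 students are unaccounted for, and the SAP has neither an analysis set nor a missing-data rule to say how they are handled.

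The size is small. Both candidate totals exceed the 46 required, so a reading that the trial is underpowered fails. A reading that the result is materially biased is also unsupported: the shift is zero if the losses came before allocation and at most about 0.10 SD for a 1 SD departure in opposite directions by arm. The 0.02 to 0.07 SD biases in the illustration depend on assumed performance-linked losses and are not evidence about this trial. That 3 students were lost after randomisation is likewise only one of two possibilities.

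**What to change.** 1. Reconcile 58 with 55, and report by arm the numbers allocated, lost (with reason and timing) and analysed.
2. Define the primary analysis set as all students actually randomised, in the arm to which they were allocated: 58 if that count is right, 55 if the 3 left earlier.
3. Analyse all available knowledge scores with a likelihood-based mixed model: time and group-by-time terms, a common pretest mean, unstructured covariance, and the group contrast at each post-test. Keep the planned ANOVA as a secondary analysis.
4. State the limits of the model. It keeps students with partial scores and is more precise. It does not remove bias when loss depends on unseen post-test scores, where it can carry slightly more than change from pretest (about 0.03 to 0.05 against 0.02 to 0.03 SD in the assumed case).
5. Reconcile the implementation and game-procedure sections on whether the intervention arm's knowledge post-test depended on exit, and report whether any student went untested for that reason.

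The cost is revised wording, a flow table, a little more analysis work and a model slightly more complex than the ANOVA. No new data are needed.
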